#### **8.1.2.1 Experimental Design**

Blood for correlative research may be drawn via port-a-cath or peripheral venipuncture. The blood draw site should remain consistent across all correlative lab timepoints for each patient throughout their participation in the trial. The first 7-10 ml blood will be excluded or used for other analyses. The following 8 ml will be collected in an EDTA tube. The EDTA tube with the blood sample will be shipped in wet ice within 2 hours of drawing for further processing at

Steele Laboratory at MGH. We will analyze the correlation between plasma cytokines and circulating myeloid cells with multiple measures of outcome (ORR, TTP, OS) in patients with borderline resectable pancreatic cancer before, during, and after treatment.

#### **8.1.2.2 Collection**

To this end we will measure circulating biomarkers at the following stages:

- (i) Pretreatment
- (ii) Throughout FOLFIRINOX therapy, including at restaging for C4 and C8
- (iii) After proton beam radiation therapy
- (iv) One month after completion of capecitabine therapy
- (v) One month post-operatively
- (vi) At the time of disease progression

Samples (2 tubes) will be collected at the following timepoints:

- a. Prior to the start of therapy
- b. Day 8 , 29, and 92 of FOLFIRINOX
- c. At restaging for Cycle 4 (and Cycle 8 if received) of FOLFIRINOX
- d. After chemoradiation OR pre-operatively
- e.. 1 month after completion of capecitabine therapy
- f. 1 month after pancreaticoduodenectomy (Whipple procedure)
- g. Within 2 weeks after radiologic progression

#### **8.1.2.3 Shipping Instructions**

The tube containing the blood should be shipped with the following information

1. Study Number at the DF/HCC
2. Patient number on the study
3. Patient's initials
4. Treating physician's name
5. Date of collection
6. Date of shipping

The tube of blood should be placed in a sealable container and placed in a box with the necessary information. The box should be marked Biohazard.

The blood will be shipped to:

[REDACTED]

#### 8.1.2 Correlative Studies: SNaPshot analysis

Diagnostic specimens (if available) will be tested using the “SNaPshot” profile, a multiplex molecular diagnostics platform which is part of routine clinical testing at the MGH Cancer Center. This assay quickly and efficiently identifies 58 separate mutations in 13 genes commonly altered in solid tumors: EGFR, KRAS, NRAS, APC, BRAF, FLT3, JAK2, Kit, Notch, PI3K, PTEN, TP53, and beta-catenin. It utilizes DNA extracted from formalin fixed paraffin embedded tumor tissue. The DNA of interest is amplified using multiplexed PCR. Genotypes are determined using a single-base extension sequencing reaction, in which allele-specific probes interrogate loci of interest and are extended by fluorescently labeled dideoxynucleotides. The allele-specific probes have different sizes and are subsequently resolved by electrophoresis and analyzed by an automated DNA sequencer. The SNaPshot profile has been validated and is being performed in a CLIA-certified lab.

Data obtained from SNaPshot will be used in exploratory analyses correlating mutational status with chemotherapy response, radiation response, and outcome.

## 8.2 Patient-reported outcomes

Pretreatment	FOLFIRINOX	ChemoRT	Post-op
At time of informed consent	Day 1 of cycles 2,4,6,8 [Week 3, 7, 11, 15]	Week 2, day1	At 3 month follow up, then every 6months for the first 2 years of follow up, then yearly until completion of year 5
EORTC QLQ-C30	EORTC QLQ-C30	EORTC QLQ-C30	EORTC QLQ-C30
ESAS-r	ESAS-r	ESAS-r	ESAS-r
HADS	HADS	HADS	HADS

### 8.2.1 Patient-reported outcomes

QOL (EORTC QLQ-C30, version 3.0), symptoms (ESAS-r), and mood (HADS) will be assessed at time of informed consent prior to neoadjuvant therapy; at weeks 3, 7, 11, and 15 of neoadjuvant chemotherapy; at week 2 of capecitabine chemoradiotherapy. During the follow up period, these measures will be assessed at the 3 month post-operative follow-up visit, then every 6 months for the first 2 years of follow up, then yearly until completion of year 5. We will include a window of +/- 2 weeks for obtaining the PROs during treatment, to cover timing adjustments for treatment delays. In follow up, these outcomes will be assessed within +/- 21 days of a correlating follow up visit. The patient may complete the questionnaires by hand or over the phone with a study team member, as well as an interpreter (if needed).

### 8.3 Health care utilization

Hospital admissions, emergency department (ED) visits, intensive care use and palliative care consultation will be monitored and recorded for each patient throughout the study.

## 9 STUDY CALENDAR

Baseline laboratory evaluations are to be conducted within seven days prior to study entry. Non-laboratory evaluations (imaging, etc) must be done  $\leq 42$  days (6 weeks) prior to study entry. All assessments must be performed prior to administration of any study medication, unless otherwise noted. All study assessments and medications should be

administered within  $\pm$  3 days of the protocol-specified date, unless otherwise noted. All follow up assessments may be performed +/- 21 days of the protocol-specified date.

**Required Data Table**

Tests and Observation	Prior to treatment	Cycles 1-8 of FOLFIRINOX/Losartan	After cycles 4 and 8 of FOLFIRINOX/Losartan (re-staging) (5)	Radiation	Follow Up Post-Proton RT (2)
Signed informed consent	X				
History	X				
Physical Examination	X	X once per cycle	X	X weekly	X
Vital Signs and performance status	X	X once per cycle	X	X weekly	X
Height/Weight/Surface Area	X	X once per cycle			
Blood Pressure Assessments and Monitoring	X	X once per cycle			
Toxicity Assessment	X	X weekly during cycle 1; every other week during subsequent cycles unless clinically indicated	X	X weekly	X
Laboratory :					
CBC/plts/diff	X (1)	X weekly during cycle 1; every other week during subsequent cycles unless clinically indicated	X	X weekly	X
Serum chemistries (Na, K, BUN, Cr, Glucose, , Calcium, Albumin, AST, ALT, Total bilirubin, Alkaline phosphatase)	X (1)	X weekly during cycle 1; every other week during subsequent cycles unless clinically indicated	X	X weekly	X

Phase II Study of FOLFIRINOX-Losartan with Short Course Radiation and Capecitabine in Locally Advanced Pancreatic Cancer August 7, 2018

Tests and Observation	Prior to treatment	Cycles 1-8 of FOLFIRINOX/Losartan	After cycles 4 and 8 of FOLFIRINOX/Losartan (re-staging) (5)	Radiation	Follow Up Post-Proton RT (2)
Creatinine clearance calculation (Cockcroft Gault)	X (1)	X weekly during cycle 1; every other week during subsequent cycles unless clinically indicated	X	X D1 and D8 of capecitabine	
CA19-9	X (1)	X Monthly	X		X
CEA	X (1)	X Monthly	X		X
Pregnancy test*	X (1)				
Research Blood for Correlative Analysis: Antifibrotic Effect (6)		X D1 (pre-treatment), D8, D29, and D92			
Tumor submitted for SNaPSHOT mutational analysis	X				
Staging:					
Chest CT Abd-pelvic CT (or MRI)	X (3)	X Mid-treatment and post-treatment	X		X (4)
Radiation Planning				X prior to RT start	
Tumor measurements (8)	X		X		X
PRO (EORTC QLQ-C30, ESAS-r, HADS) (7)	X	X	X	X	X

Notes

- (1) Pre-study Laboratory values need to be obtained within 7 days of study entry.
- (2) Post-study follow up schedule is clinic visit and labs every three months until disease progression. The first visit will be 1 month after surgery. Then follow up visits will be every 3 months. CT scans will be at least every six months for the first two years and yearly for years 3-5. All follow up assessments will be performed +/- 21 days of protocol-specified date.
- (3) Staging CT or MRIs need to be obtained within 42 days of study entry
- (4) CT scans will be performed at least every 6 mo for the first 2 years and yearly for years 3-5. All follow up CT scans will be performed +/- 21 days of protocol-specified date
- (5) Restaging scans can be performed after pump disconnect during FOLFIRINOX cycles 4 and 8.

- (6) Blood for correlative studies will be obtained with clinical labs at pretreatment, day 8 of Cycle 1 FOLFIRINOX, at mid-FOLFIRINOX restaging, at post-FOLFIRINOX restaging, after chemo radiation therapy, 1 month after completion of capecitabine therapy, 1 month post-operatively (if surgery is performed), and within two weeks of radiographic progression (these blood draws are optional).
- (7) See section 8.2 for patient reported outcomes assessment timing.
- (8) Tumor measurements will be completed within +/-6 months of the scans. These measurements will be completed by the overall PI of the study.

## **10 MEASUREMENT OF EFFECT**

### **10.1 Evaluation Of Response**

#### 10.1.1 Imaging Response: Standard Imaging

Response to therapy and/or progression after induction chemotherapy with FOLFIRINOX will be evaluated in this study using the international criteria proposed by the RECIST (Response Evaluation Criteria in Solid Tumors) committee. Changes in only the largest diameter (unidimensional measurement) of the tumor lesions are used in the RECIST criteria. In the event that CT staging cannot be utilized, restaging MRI will be the substitute modality.

#### 10.1.2 Progression-free survival

Progression-free survival will be defined as the time from the start date of protocol therapy to first objective documentation of progressive disease (distant or local) or death. Patients who die without a reported prior progression will be considered to have progressed on the day of their death.

#### 10.1.3 Time to death

Time to death will be calculated as the time from the start date of protocol therapy to date of death

### **10.2 Definitions**

10.2.1 Evaluable for toxicity. All participants who receive at least one dose of study treatment will be evaluable for toxicity from the time of their first treatment.

10.2.2 Evaluable for objective response. Only those participants who have measurable disease present at baseline, have completed induction chemotherapy, and have had

their disease re-evaluated will be considered evaluable for response. These participants will have their response classified according to the definitions stated below.

(Note: Participants who exhibit objective disease progression or die prior to the end of induction chemotherapy will also be considered evaluable.)

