Based on findings from preliminary studies, we propose here to evaluate the changes in blood circulating SDF1 $\alpha$  and circulating myeloid cells throughout the treatment course to explore potential associations between the changes in these biomarkers and resistance to treatment. In exploratory studies, we will evaluate several other cytokines using multiplex protein array (Meso-Scale Discovery, Inc.). We will use ELISA kits to measure plasma levels of collagen I (Cosmo Bio Co.), collagen IV (Echelon BioSciences Inc), human cross-linked carboxy-terminal telopeptide of collagen I (Cusabio), ATII (Assaypro), CTGF, TGF $\beta$ 1, TSP-1, osteopontin, soluble vascular endothelial growth factor receptor 2, angiopoietin 2 and SDF-1 $\alpha$  (R&D Systems). Multiplex ELISA plates (Meso-Scale Discovery) will be used to analyze plasma levels of VEGF, placenta growth factor (PIGF), soluble VEGF receptor 1 (sVEGFR1), basic fibroblast growth factor (bFGF), VEGF-C, VEGF-D, sTie2, tumor necrosis factor alpha (TNF- $\alpha$ ), and IL-1 $\beta$ , IL-4, IL-10, and IL-13. Granulocytes (CD11b+Ly6G+CD115-) will be enumerated in fresh samples using a standard flow cytometry protocol. In addition, we will analyze the correlation between plasma SDF1 $\alpha$  and circulating myeloid cells with multiple measures of outcome (ORR, TTP, OS) in pancreatic cancer patients after losartan treatment.

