## 14 STATISTICAL CONSIDERATIONS

### 14.1 Study Design

14.2 **The single-arm protocol is a phase II study to investigate combining Losartan with FOLFIRINOX for induction chemotherapy followed by restaging and radiation therapy with capecitabine in the treatment of patients with locally advanced pancreatic cancer. The primary endpoint is the rate of R0 (negative margin) resection determined by final pathology of the surgical specimen. Our historical data show a <10% rate of R0 resection among unresectable patients treated with induction chemotherapy followed by chemoradiation. The protocol will have demonstrated an improvement in efficacy if R0 resection were achieved in at least 9 of 50 patients. The decision rule is associated with 91% power if FOLFIRINOX-Losartan with short-course radiation and capecitabine were to improve the R0 resection rate to 25%. In contrast, the probability of a type 1 error is only 6% if the underlying rate of R0 resection were truly the same as the historical level of 10%. All protocol patients who start induction chemotherapy will be included in the denominator for R0 resection analysis, including those who do not undergo surgery due to early progression or other reasons. Sample Size/Accrual Rate** The accrual goal of 50 patients is projected to be enrolled over a total period of 4.5 years. The estimate is based on the overall rate of accrual based on the first 32 patients since the protocol was first open to patient entry. Therefore, we project the enrollment of the remaining 18 patients will require no more than 1.5 years.

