### 14.3 Analysis of Secondary Endpoints

- 14.3.1 **Progression-free survival:** All patients who start induction chemotherapy will be analyzed based on the definition in Section 10.1.2. The progression-free survival duration of patients who are alive and progression will be censored at their date of last follow-up. The Kaplan-Meier method will be used to estimate progression-free survival with 90% confidence intervals constructed by Greenwood's formula.
- 14.3.2 **Overall survival:** Overall survival will be defined as the duration between the start date of protocol therapy and death. The survival time of patients who are not known to have died will be censored at the date they are last known to be alive. The Kaplan-Meier method will be used to estimate overall survival estimation with 90% confidence intervals constructed by Greenwood's formula.
- 14.3.3 **Toxicities:** All patients who begin induction chemotherapy will be included in the toxicity profile of Losartan combined with induction FOLFIRINOX. Summaries of toxicities will include the frequency and proportion of patients experiencing each toxicity, as well as summaries by toxicity category and toxicity grade. We shall report separately the additional treatment-related toxicity following radiation in patients who do not have progressive disease at the restaging interval after induction chemotherapy.
- 14.3.4 **Downstaging:** A fraction of patients may proceed to surgical resection following the conclusion of protocol therapy if the tumor shrinkage were sufficient to be considered resectable. The rate of downstaging to surgical resection will be determined as the proportion of initially unresectable patients who eventually undergo pancreaticoduodenectomy or distal pancreatectomy. The pathologic downstaging rate will be calculated as the proportion of resected patients with the primary tumor and nodes downstaged based on final pathology of the surgical specimen.
- 14.3.5 **Correlation of biomarkers with outcome:** Correlative studies will be conducted to characterize circulating collagen and angiogenesis biomarkers (8.1.1), as well as somatic genetic mutations characterized by the SNaPshot platform (8.1.2). Due to the modest patient numbers, analysis will be limited generally to two-group comparisons of each

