### **4.3 Reporting and Exclusions**

All patients who begin protocol treatment will be included in the primary and the relevant secondary endpoints.

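### The objective-response set leaves out patients who stop induction early without progressing, so any reported response rate is selected on tolerance and is likely, though not certainly, too high

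*Combined protocol and SAP*

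**What the plan says.** Section 10.1.1 commits the trial to assessing response: "Response to therapy and/or progression after induction chemotherapy with FOLFIRINOX will be evaluated in this study". Section 10.2.2 then defines who counts. The set is "Only those participants who have measurable disease present at baseline, have completed induction chemotherapy" and have been re-evaluated, and only these patients have a response classified. A note widens it: "Participants who exhibit objective disease progression or die prior to the end of induction chemotherapy will also be considered evaluable".

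Other endpoints are analysed in everyone who starts. For the primary endpoint (Section 14.1), "All protocol patients who start induction chemotherapy will be included in the denominator for R0 resection analysis". For progression-free survival (Section 14.3.1), "All patients who start induction chemotherapy will be analyzed based on the definition in Section 10.1.2". Section 14.3.3 takes the same approach to induction toxicity. The paragraph on reporting and exclusions (numbered 4.3, at the end of Section 14) gives the general rule: "All patients who begin protocol treatment will be included in the primary and the relevant secondary endpoints".

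Objective response is not among the objectives in Sections 1.2 and 1.3 and has no analysis paragraph in Section 14. It is used in the optional correlative work. Section 8.1.1 relates plasma and cellular markers to "multiple measures of outcome (ORR, TTP, OS"), Section 8.1.2.1 repeats this, and Section 8.1.2 relates mutation status to chemotherapy response.

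**The concern.** A patient can leave induction before cycle 8, alive and without progression, by several routes: an unacceptable adverse event, intercurrent illness or withdrawal (Section 5.5), or un-enrolment for persistent low blood pressure or recurrent high potassium on losartan (the hypotension and hyperkalemia paragraphs of Section 6.2). None of these patients meets the completion condition, and the note does not bring them back.

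Membership of the response set therefore depends partly on how well the patient tolerated treatment, including the agent under study. Section 5.1 schedules a restaging scan after cycle 4, so some of these patients will have usable response data that the definition sets aside. Under Section 10.6.1 a partial response first seen at cycle 4 starts the clock for duration of response, yet if that patient then stops for toxicity, Section 10.2.2 makes the same patient not evaluable.

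At stake are the interpretation of any published response rate and of the exploratory correlations that use response as an outcome.

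**Working it through.** **Primary rule, as a reference point.** Success is declared if "R0 resection were achieved in at least 9 of 50 patients". Exact binomial tails with n = 50 are:
- P(X ≥ 9 | 0.10) = 0.0579, against the stated 6%.
- P(X ≥ 9 | 0.25) = 0.9084, against the stated 91%.

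Both figures reproduce. They already rest on all starters, so the response definition does not touch them. The plan states no figure for response rate.

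**Who is in and who is out under Section 10.2.2** (measurable disease at baseline assumed).

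| Course during induction | In the response set? |
|---|---|
| Completes cycle 8 and is rescanned | Yes |
| Progresses or dies before the end of induction | Yes, by the note |
| Stops for toxicity, withdrawal or un-enrolment; cycle 4 scan available | No |
| Stops for the same reasons before any scan | No |

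**Formula.** Let R be responders among 50 starters, k the number dropped, and r the number of dropped patients with a recorded response.
- All-starters rate: R/50.
- Rate in the Section 10.2.2 set: (R − r)/(50 − k).
- The second exceeds the first when 50(R − r) > R(50 − k), that is, when r/k < R/50. The rate is inflated only if the dropped patients respond less often than starters as a whole.

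**Inputs.** The documents give neither k nor r, and the trial assumes no response rate. I take R = 15 (30%), close to the 31% partial response rate that Section 2.2.2 reports for FOLFIRINOX in metastatic disease, and assume that all 50 have measurable disease.

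| Dropped (k) | Responders among them (r) | Rate in the set | Change from 30.0% |
|---|---|---|---|
| 5 | 0 | 15/45 = 33.3% | +3.3 points |
| 5 | 2 | 13/45 = 28.9% | −1.1 points |
| 10 | 0 | 15/40 = 37.5% | +7.5 points |
| 10 | 3 | 12/40 = 30.0% | none |
| 10 | 4 | 11/40 = 27.5% | −2.5 points |

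**Sensitivity to R.** With R = 16 (32.0%) and no responders dropped, k = 3, 5, 10 and 13 give 16/47 = 34.0%, 16/45 = 35.6%, 16/40 = 40.0% and 16/37 = 43.2%. With k = 10 and r = 3 or 4, the results are 13/40 = 32.5% and 12/40 = 30.0%.

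**Likely direction.** A patient who stops before the cycle 4 scan, for example one un-enrolled at the Day 8 blood pressure check, has no recorded response, so r = 0 for that patient. Removing such patients can only raise the rate relative to an all-starters count. Patients who stop after cycle 4 can move it either way.

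**The case against.** The strongest defence is that the set is openly defined, that a response-evaluable population is a legitimate choice of analysis set, and that requiring completed induction fits the timepoint in Section 10.1.1, which speaks of response after induction. The most obvious route to inflation is already closed, because early progressors and deaths are kept. Response is not a listed endpoint. The correlative work is optional, and Section 14.3.5 specifies tests only for progression-free and overall survival and calls the analysis exploratory. All of this stands, and it limits the importance of the point.

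Two stronger readings are tempting, and the documents support neither.

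- A reader might infer that Section 10.2.2 contradicts the all-starters rule. That rule covers the primary and the relevant secondary endpoints. One could argue that the biomarker objectives (1.3.7 and 1.3.8) bring response in under the word outcome, but Section 14.3.5 tests those objectives on survival endpoints. What can be shown is a different approach for response, with nothing in Section 14 to settle its denominator.
- A reader might infer that the rate is biased upward as a matter of fact. A cycle 4 responder who then stops for toxicity leaves the numerator as well as the denominator, and the table shows the effect vanishing or reversing.

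What the defence does not answer is that exclusion depends on an event after the start of treatment, and that patients with a valid scan are set aside.

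**Conclusion.** The point holds as a cheap improvement. Section 10.2.2 selects the response set partly on tolerance of treatment and discards some available cycle 4 assessments, unlike the plan's handling of R0 resection, progression-free survival and toxicity. The likely effect is a response rate that is somewhat too high: 3.3 to 7.5 points from a base of 30% if 5 to 10 non-responders are dropped. It is zero or negative if about 30% or more of those dropped had already responded. These sizes rest wholly on assumed counts of responders and early stoppers.

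The exploratory biomarker-response and mutation-response correlations would use the same selected patients. R0 resection, progression-free survival, overall survival, toxicity and the 9-of-50 rule are unaffected.

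**What to change.** In Section 10.2.2, make the main response analysis all patients with measurable disease at baseline who start treatment. Use any post-baseline scan, stating that the cycle 4 scan counts. Show patients with no assessment as Unknown, the category already provided in Section 10.5.1.5, and count them as non-responders in the rate. Report the number and reasons for these cases. Keep the present evaluable set as a supportive analysis, so that the two rates can be read side by side. Add a line to Section 14 naming the denominator, and apply the same set to the correlations in Sections 8.1.1, 8.1.2.1 and 8.1.2.

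The cost is wording only: no new patients, visits or data. The downside is a possibly slightly lower reported response rate.
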